8. RISK AND BENEFIT ASSESSMENT

The study involves the creation of an arteriovenous fistula, therefore the risks of participating in this research include the risks inherently associated with a standard AV fistula creation which may include bruising, numbness, tingling and/or coolness in the extremity, thrombosis, stenosis, failure to mature, additional interventions, venous hypertension, swelling, irritation or pain, bleeding/hemorrhage, hematoma, seroma, wound problem, fever, steal syndrome, ischemia, embolism, infection, increased risk of congestive heart failure, nerve damage, vessel damage, pseudoaneurysm, compartment syndrome, heart problems such as arrhythmias, burns, problems due to sedation or anesthesia, sepsis, allergic reaction, or death.

With the implantation of any foreign material such as a radiologic marker (EchoMark), there is risk of allergic reaction, inflection, inflammation, migration, or extrusion. Given the biocompatibility data collected by the company and the extensive prior use of the material in medicine, the probability of such risk is low. The safety of the device for general use has already been evaluated by the FDA during the clearance process for EchoMark and there has been a prior multicenter study in AV fistula patients that has shown maturation success rates that were in line with recent literature. There is also a possibility that the fistula may slide out of the EchoMark, which may prevent the EchoSure device from measuring the flow, diameter and depth accurately. When the EchoMark implant is secured properly the likelihood of this risk is low and standard of care methods for assessing the fistula are still available making the severity low. There is risk that the ultrasound scan may create mild discomfort for the subject on the wound site. The likelihood and severity of this risk is low.

Prior experience in the AV population captured adverse events including infection and seroma. All subjects are to be closely monitored for signs of an infection or seroma. If the subject begins to exhibit signs of infection, inflammation or extrusion, a clinical decision will be made by the team if the risk from the implantable device requires removal of the device. In these cases, the implantable device will be removed, and the subject will be monitored with the institution's standard of care, including physical exam and possibly ultrasound. The event will be tracked until the symptoms are resolved.

There is potential risk of loss of subject confidentiality in the event of a data breach. Protections are in place to minimize the risk. No protected health information (PHI), such as subject names, medical record numbers, or other identifying information which could be linked to a subject will be stored in the database. A subject ID number will be assigned to medical record information stored in the database. Information linking the subject ID to subject PHI will be store separately in a secure location, accessible to study personnel only.

Participation in the clinical study does not provide any guarantee of benefit to the subject. However, the study follows existing Standard of Care with additional touchpoints. The study involves at least monthly post-op visits with the physician, providing the ability to detect any issues that may arise from the study and can then be addressed in a timely fashion. Second, subjects will receive additional care above and beyond the Standard of Care, including extra physical examinations and ultrasound assessments.

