NUMBER OF Clinical Sites	Up to 6 sites within in the United States will be evaluated, qualified, and selected for participation.										
PROCEDURE AND FOLLOW-UP:	All subjects that receive an EchoMark LP will be evaluated at the following time-points: • 15 days (+/- 7 days) • 30 days (+/- 7 days) • 60 days (+/- 15 days) • 90 days (+/- 15 days) • 120 days (+/- 15 days) • 150 days (+/- 15 days) • 150 days (e month) (+/- 15 days) • 12 Month (1 Year) (+/- 15 days) • 15 Months (+/- 15 days) • 18 Months (+/- 15 days) • 24 Months (+/- 15 days) • 24 Months (+/- 15 days) Except for the 180 day (6 month), 12 month (1 year), 15 Month, 18 Month, and 24 Months visits, each visit will include a physical exam, Duplex scan, EchoSure scan, and assessment for adverse events. The monthly EchoSure scans will be suspended after the 120-day (4 month) visit or once radiographic maturation is achieved, whichever is longer, but clinical follow-up and Duplex will continue per the above schedule. The 180-day (6-month) and 12 month (1 year)visits will include a physical examination, Duplex scan for patency, and an assessment for adverse events. The 15 Month, 18 Month, and 24 Month visits will include a physical examination, Duplex scan for patency, and an assessment for adverse events. The 15 Month, 18 Month, and 24 Month visits will include capture of medical history since the last visit, a duplex scan, information on any fluid collection observed on the Duplex scan, and an assessment for any adverse events. EchoSure scans will be completed by study personnel who do not have prior ultrasound training and are representative of non-expert users. Subjects that are consented but do not receive the EchoMark LP will be considered a screen failure, and can be replaced.										
Primary Endpoint	The primary safety and feasibility endpoints are as follows:										
	Primary Safety:										

	 Composite of new major device related adverse events (MAEs) at 30 days post EchoMark LP implantation, as adjudicated by the Clinical Events Committee (CEC), including: Device or procedure-related death Device related infection Device related interventions Device related hospitalizations Fistula failure Fistula rupture Aneurysm 							
	After the close of the final 90-day visit window, all evaluable subjects will be summarized and expansion to a pivotal trial will be requested under a new IDE.							
	Primary Feasibility (Technical Success):							

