7.6 Pre-Maturation Follow-up at 15, 30, 60, 90, 120, 150 Days

Subjects will have follow-up visits at 15 (+/- 7 days), 30 (+/- 7 days), 60 (+/- 15 days), 90 (+/- 15 days), 120 (+/- 15 days), and 150 (+/- 15 days) days from the baseline procedure, including a physical exam, duplex imaging, EchoSure scan, external EchoMark measurement, medical history, and adverse event monitoring. The EchoSure scans will be suspended after the 120 day (4 month) visit or once radiographic maturation is achieved,

whichever is longer. Radiographic maturation is defined as 500mL/min and a 5 mm diameter. The monthly clinical follow-up and duplex imaging will continue per the follow-up schedule. The physical exam will include assessing the fistula for bruit and thrill. The medical history will include all interventions, cannulation history including any attempts, and the most recent Kt/V, CBC, Serum Chemistry, Calcium, Phosphorous, Magnesium, Total Protein, Albumin, PTH. EchoSure scans will be completed by study personnel who do not have prior ultrasound training, are representative of non-expert users, and have been delegated on the delegation of authority log. Duplex and EchoSure scans will include:

- A total of three (3) EchoSure scans performed at the site of the EchoMark. Volume flow, diameter, and depth data to be recorded.
- A total of three (3) limited DUS scans performed at the site of the EchoMark. DUS will be performed in transverse Bmode and longitudinal view. Volume flow, diameter, depth, and distance from scan area to anastomosis will be recorded.
- A total of three (3) limited DUS scans performed at the cannulation zone in transverse Bmode and longitudinal view. Volume flow, diameter, and depth, will be recorded.
- The 9 Duplex images will be de-identified and undergo quality control checks performed by an Independent RVT.
- A duplex exam of the fistula from the EchoMark location and beyond to assess for the presence of stenotic lesions. If a lesion is present, capture and save an image showing a longitudinal view of the fistula segment with the stenosis, note the location of the stenosis in relation to the anastomosis and EchoMark, and track the stenosis as an adverse event.
- A duplex scan of the brachial artery to assess flow and diameter, capture a PW image showing the flow and diameter measurements.

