- Limited DUS scan performed at the site of EchoMark to determine EchoMark visibility including:
 - 1 BMode, transverse view of EchoMark at center
 - 1 BMode, transverse view of EchoMark at distal edge
 - 1 BMode, Transverse view of EchoMark at proximal edge
 - 1 BMode, Longitudinal view centered over vessel showing full length of EchoMark.
- A duplex exam of the fistula from the EchoMark location and beyond to assess for the presence of stenotic lesions or a fluid collection. If a lesion is present, capture and save an image showing a longitudinal view of the fistula segment with the stenosis, note the location of the stenosis in relation to the anastomosis and EchoMark, and track the stenosis as an adverse event. If a fluid collection is present, capture and save an image noting the location from the anastomosis and the size and volume.
- A duplex scan of the brachial artery to assess flow and diameter, capture a PW image showing the flow and diameter measurements.

7.9 15 Month, 18 Month, and 24 Month (+ 15 Days) Follow-up

All subjects who are willing to reconsent to longer-term follow-up will have a follow-up visit at 15 months, 18 months, and 24 months after baseline procedure. Follow-up visits will include a captures of medical history since the last visit, Duplex scan, and adverse event monitoring. The Duplex scans will include:

- Limited DUS scan performed at the site of EchoMark to determine EchoMark visibility including:
 - 1 BMode, transverse view of EchoMark at center
 - 1 BMode, transverse view of EchoMark at distal edge
 - o 1 BMode, Transverse view of EchoMark at proximal edge
 - 1 BMode, Longitudinal view centered over vessel showing full length of EchoMark
- A duplex exam of the fistula from the EchoMark location and beyond to assess for the presence of a fluid collection. If a fluid collection is present, capture and save an image noting the location from the anastomosis and the size and volume.

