11.2.8.6 Clinical Maturation Success Rate

Clinical maturation success rate is defined as the percentage of subjects that achieve clinical maturation by end of study.

Clinical maturation is defined as 75% of dialysis sessions with 2 needle cannulation for 4 weeks.

11.2.8.7 6-Month Patency Rate

6-month patency rate is defined as the percentage of subjects that have patent access at 6 months if both radiographic and clinical maturation definitions have been met.

6-month patency rate as defined by the status (yes/no) of an arteriovenous dialysis access with detectable blood flow through and beyond the anastomosis shown by either an imaging modality or physical examination (presence of a palpable thrill or audible bruit along some point of the arteriovenous dialysis access beyond the arteriovenous anastomosis).

11.2.8.8 12-Month Patency Rate

12-month patency rate is defined as the percentage of subjects that have patent access at 12 months if both radiographic and clinical maturation definitions have been met.

12-month patency rate as defined by the status (yes/no) of an arteriovenous dialysis access with detectable blood flow through and beyond the anastomosis shown by either an imaging modality or physical examination (presence of a palpable thrill or audible bruit along some point of the arteriovenous dialysis access beyond the arteriovenous anastomosis).

11.2.8.9 30-day occurrence of Interventions or Hospitalizations

Occurrence of events occurring within 30 days of implantation that require reinterventions (open or endovascular), hospitalizations, or prolongation of existing hospitalization

11.2.8.10 Occurrence of Events:

Occurrence is defined as the overall number of each event listed below that occur in the defines time period.

- Occurrence of reported reduction of blood flow that prevents the ability to cannulate or requires further assessment and/or intervention from baseline to 12 months.
- Occurrence of reported inability to cannulate fistula beginning once the fistula is deemed radiographically and clinically mature to 12 months.
- Occurrence of the development of steal syndrome from baseline to 12 months.
- Occurrence of bleeding requiring surgical intervention (including PRBC transfusion) from baseline to 12 months.
- Occurrence of infiltration requiring procedural intervention from baseline to 12 months.
- Occurrence of hematoma requiring procedural intervention from baseline to 12 months.

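### Seroma is named as a known harm to be monitored closely, but no visit before day 180 directs the Duplex exam at fluid, and a non-serious seroma has no named endpoint

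*Combined protocol and SAP*

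**What the plan says.** Section 8 states that "Prior experience in the AV population captured adverse events including infection and seroma" and then that "All subjects are to be closely monitored for signs of an infection or seroma". It gives no method or visit for the monitoring. The same section also lists seroma among the general risks of standard fistula creation.

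The discharge scan (Section 7.5) records flow, diameter and depth where feasible. For days 15 to 150, Section 7.6 calls for "A duplex exam of the fistula from the EchoMark location and beyond to assess for the presence of stenotic lesions". Sections 7.7 (day 150, radiographically mature) and 7.10 (fistula outside the EchoMark) set the same target. Fluid enters at Section 7.8, for the 180-day and 12-month visits, where the exam is "to assess for the presence of stenotic lesions or a fluid collection", followed by: "If a fluid collection is present, capture and save an image noting the location from the anastomosis and the size and volume". Section 7.9 asks for the same at months 15, 18 and 24, and the synopsis lists "information on any fluid collection observed on the Duplex scan" for those visits. For the 180-day and 12-month visits, however, the synopsis describes the Duplex only as a check of patency.

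The primary safety composite (Section 4.2.1) has seven components, none of them seroma or fluid collection. The event list in Section 11.2.8.10 opens with "Occurrence is defined as the overall number of each event listed below that occur in the defines time period". It has lines for hematoma, infection (two), infiltration, bleeding, steal syndrome and pain, but none for seroma. Every item on it closes at 12 months or earlier.

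**The concern.** Section 8 pairs two harms from prior use, and only one is followed through. Infection is a component of the primary composite and has two observational lines. Seroma has neither a line of its own nor, for roughly the first six months, an imaging instruction.

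What is at stake is how a low or zero count would be read. The primary safety result is taken at 30 days, and the summary after the 90-day window supports the request for a pivotal trial. If seroma reaches those tables only when someone notices and reports it, an absence of reports says little about small or asymptomatic collections around the implant. A first directed look near six months cannot date onset and will miss collections that have already resolved, unless they were noticed incidentally.

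**Working it through.** **1. Duplex targets side by side (Table 1 and Sections 7.5 to 7.10).**

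| Visit | Section | Fluid named as a target? |
|---|---|---|
| Discharge | 7.5 | No (flow, diameter, depth) |
| Days 15, 30, 60, 90, 120, 150 | 7.6 | No (stenosis, plus measurements) |
| Day 150 if mature | 7.7 | No (stenosis, patency, marker visibility) |
| Fistula outside EchoMark, before day 180 | 7.10 | No (stenosis, patency, marker visibility, measurements) |
| Day 180, month 12 | 7.8 | Yes |
| Months 15, 18, 24 | 7.9 | Yes |

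Post-operative Duplex exams in Table 1: 1 (discharge) + 6 (days 15 to 150) + 2 (day 180, month 12) + 3 (months 15, 18, 24) = 12. Without a fluid target: 1 + 6 = 7. By the day-30 visit: 3 of 3. By the day-90 visit: 5 of 5.

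**2. Timing within a subject.**
- The 90-day window closes at 90 + 15 = day 105.
- By Table 1 the 180-day window opens at 180 − 15 = day 165. The heading of 7.8 prints only + 15 days, which would make it day 180; the two should agree.
- First directed look after day 30: 165 − 30 = 135 days at the earliest (150 on the other reading).
- First directed look after the 90-day window closes: 165 − 105 = 60 days at the earliest (75 on the other reading).

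These gaps are per subject. In calendar time, a subject implanted at least 60 days before the last one could have had a 180-day scan by the time of the 90-day summary. That scan would still say nothing about when a collection arose. The documents give no enrolment period.

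**3. Routes by which a seroma can be counted now.**
- General AE reporting: inquiry at study visits, all AEs documented (9.5), CEC adjudication of reported events (12.7), summaries by subject and listings (11.2.1).
- Primary analysis: a device- or procedure-related SAE counts against the 30-day result (11.2.6).
- Composite: a seroma leading to device-related infection, intervention or hospitalization enters under that heading (4.2.1).
- 30-day observational item: one requiring reintervention or hospitalization (4.2.3).

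A non-serious seroma with none of these consequences has only the first route. From day 180, Section 7.8 says a stenosis is to be tracked as an adverse event but gives no such instruction for fluid. The month 15 to 24 findings therefore reach the AE listings only if someone reports them as AEs, and they reach no listed endpoint.

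**4. Illustration of what a zero count could mean.** The plan has no figure on this point to reproduce, and no seroma rate. With n = 20 (the plan says up to 20, plus roll-ins):
- Exact 95% upper limit for 0/20, two-sided: 1 − 0.025^(1/20) = 16.8%; one-sided: 1 − 0.05^(1/20) = 13.9%. Both presume that every subject was examined for it.
- Chance of at least one recorded case, with true rate p and fraction s of cases captured: 1 − (1 − p·s)^20.

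| Assumed p | s = 1 | s = 0.5 | s = 0.25 |
|---|---|---|---|
| 5% | 64% | 40% | 22% |
| 10% | 88% | 64% | 40% |
| 20% | 99% | 88% | 64% |

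Both p and s are assumptions.

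**The case against.** A reader might infer that the trial will hold no seroma data before day 180, or that no endpoint could ever count a seroma. The documents do not support either reading. AEs are asked about at study visits and all are documented, physical exams run through 12 months, and step 3 of the working shows how a consequential seroma enters the primary and observational results.

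Nor does the plan contradict Section 8, which promises monitoring for signs and not imaging or a dedicated endpoint. Frequent visits with an exam and AE inquiry can meet that wording.

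The implant site is also imaged early. Section 7.6 calls for three limited scans at the EchoMark in transverse B-mode and longitudinal view at each visit from day 15, and the study images go to the Independent RVT. A visible collection could be noticed and reported. This stands, with two limits: the RVT's listed checks (12.8) concern calipers and flow settings, and the physical exam content named for these visits is bruit and thrill.

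Finally, seroma is also a risk of fistula surgery itself. In a small single-arm study, early asymptomatic fluid will be hard to attribute to the device. That is a good reason to leave it out of the primary composite, but not a reason to leave it uncounted.

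**Conclusion.** The point holds as a gap in targeted ascertainment. Seven of 12 post-operative Duplex exams, including every one through day 90, have no fluid target, and non-serious seroma has no named endpoint. For a harm already seen with the device, the 30-day result and each subject's data through day 90 rest on unsolicited reports and physical exam. At an assumed true rate of 10%, capturing half of cases instead of all would lower the chance of recording at least one in 20 subjects from 88% to 64%.

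It would go too far to say that the primary safety result is wrong or that the composite must include seroma; nothing in the documents shows that. The conclusion also rests on the documents supplied. The detailed Duplex protocol sits in the Investigator's Brochure (cited in Section 7.2), and neither it nor the case report forms and charters were available. A fluid field in any of them would narrow the gap. This is a worthwhile, inexpensive improvement and not a fatal flaw.

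**What to change.** - Carry the fluid-collection instruction of Section 7.8 (image, location, size, volume) into the Duplex exam already done under 7.6, 7.7 and 7.10, and into 7.5 where the discharge scan is feasible.
- Add *occurrence of seroma or peri-implant fluid collection* to Sections 4.2.3 and 11.2.8.10 as an observational event, reported at 30 days, 90 days and 12 months, and at 24 months for reconsented subjects. Include it in the 90-day summary. Report subjects as well as events, because one collection may be seen on several scans and 11.2.8.10 counts overall numbers.
- Leave the primary composite unchanged.
- Reconcile the synopsis description of the 180-day and 12-month Duplex with Section 7.8, and the visit window in the 7.8 heading with Table 1.
- Check the Investigator's Brochure Duplex protocol and the case report forms for an existing fluid field first.

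The cost is one added instruction in existing exams, one form field and one table row, with no extra visit. The downside is that more small asymptomatic collections will be recorded, some reflecting the fistula surgery and not the device, so the safety table may look somewhat less favourable.

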9. ADVERSE EVENTS

Adverse event means any untoward medical occurrence associated with the use of an intervention in humans, whether or not considered intervention-related (21 CFR 312.32 (a)).

9.1 Serious Adverse Event

An adverse event (AE) or suspected adverse reaction is considered "serious" if, in the view of either the investigator or sponsor, it results in any of the following outcomes: death, a life-threatening adverse event, in subject hospitalization or prolongation of existing hospitalization, a persistent or significant incapacity or substantial disruption of the ability to conduct normal life functions, or a congenital anomaly/birth defect. Important medical events that may not result in death, be life-threatening, or require hospitalization may be considered serious when, based upon appropriate medical judgment, they may jeopardize the participant and may require medical or surgical intervention to prevent one of the outcomes listed in this definition.

9.2 Unanticipated Adverse Device Effects (UADE)

A UADE is considered "any serious adverse effect on health or safety or any life-threatening problem or death caused by, or associated with, a device, if that effect, problem, or death was not previously identified in nature, severity, or degree of incidence in the investigational plan or application (including a supplementary plan or application), or any other unanticipated serious problem associated with a device that relates to the rights, safety, or welfare of subjects."

9.3 Severity of an Adverse Event

For adverse events (AEs) the following guidelines will be used to describe severity.

- Mild Events require minimal or no treatment and do not interfere with the participant's daily activities.
- Moderate Events result in a low level of inconvenience or concern with the therapeutic measures. Moderate events may cause some interference with functioning.
- Severe Events interrupt a participant's usual daily activity and may require systemic drug therapy or other treatment. Severe events are usually potentially life-threatening or incapacitating.

